records in combination with continuous glucose monitoring (CGM) to capture free-living EI and monitor adherence to the program. In addition, we will evaluate the effects of TRF on free-living PA and sleep. In the Bath Breakfast Project, individuals were found to have greater physical activity energy expenditure when consuming as compared to skipping breakfast^{21,23}. Also, sleep restriction alters food intake and habitual physical activity³³, but less is known about how dietary patterns affect sleep. Food intake near the onset of sleep is negatively associated with sleep quality, 4-6 so it may be hypothesized that the early TRF paradigm could improve sleep. Finally, we will measure sleep and nocturnal energy metabolism in a subset of subjects (n=5) in each group (RCD and RCD+TRF) following the intervention and correlate these measures with longitudinally determined weight regain at 6 months. These studies will allow us to start collecting data on physiological processes that might promote weight regain or support weight maintenance following weight loss. TRF studies in rodents show favorable adaptive responses to nocturnal nutrient oxidation that appear to be protective against metabolic challenges such as high fat feeding^{8,9,26}. If these adaptive responses in nocturnal nutrient metabolism observed in rodents translate to humans, then TRF may be a potent strategy for promoting weight maintenance in reduced obesity, the most vexing problem facing obesity treatment.

III. Preliminary Studies/Progress Report:

The idea to study TRF comes from our group's experience with breakfast skipping studies^{22,34}. While our study²², as well as other interventional trials^{21,23} failed to show weight loss with breakfast skipping, these studies did not evaluate the timing of food intake throughout the rest of the day. In contrast, we³⁴ and others³⁵ have shown that breakfast skipping was acutely associated with an increased insulin response to lunch, and other studies have shown increased glucose variability²¹ and insulin resistance²³ with breakfast skipping. This, along with emerging research relating to the meal timing and the circadian regulation of metabolic systems³⁶, provides a physiological basis for potential metabolic benefits of TRF.

IV. Research Methods

A. Outcome Measure(s):

Primary Outcomes:

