Nocturnal energy metabolism: Participants will be invited to spend a night in the UCH whole room calorimeter for the measurement of nocturnal energy metabolism. We aim to perform approximately n=5 room calorimeter studies per group depending on budget. To facilitate recruitment for the optional procedure, the evening spent in the room calorimeter could be completed any night following study enrollment and prior to starting the weight loss intervention (except for during the 7-day free-living assessment of meal timing. El. and activity described above). Prior to the room calorimeter stay, participants will be asked to perform 3-days of sleep logs and cell phone based meal logging with time stamps to ensure meal and sleep timing are consistent prior to the chamber stay. Subjects will be provided an energy balance diet (calculated as RMR times an individually determined activity factor) on the day of the overnight chamber stay at baseline. The macronutrient composition of the diet will be the same at baseline and at the 12week follow-up: carbohydrate = 50%, fat = 35%, and protein = 15% (percent daily caloric intake:25% breakfast, 30% lunch, 35% dinner, and 10% afternoon snack). The meals will be eaten over a 12 hour period as follows: subjects will be asked, "when can you eat your first meal in the morning? (1, 2, or 3 hours after waking?)". This clock time will be T0. The meal times are then set at +5 (lunch), +8 (snack). +11.5 (dinner) after T0. . Subjects will arrive at the CTRC at least 2 hours before dinner and be placed in the room calorimeter at their habitual bedtime for measurement of nutrient oxidation and energy expenditure as previously described⁵⁵. Substrate oxidation will be calculated from urine nitrogen excretion, O2 consumption and RQ based on published equations⁵⁶. The chamber stay will be repeated at the 12-week follow up (between

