weeks 12 and 16). The energy content of the diet will be determined based on RMR measured at baseline and reduced by 10% (as per weight loss intervention dietary prescription). In addition, participants in the TRF group will be asked to eat all food within their chosen 10-hour eating window as follows: where their habitual breakfast time is T0, Lunch=+4h, snack=+6h, and dinner=+9.). Participants in the RCD group will eat all meals within the same 12-hour eating window as was followed at baseline. The *rationale* for measuring nocturnal metabolism is that previous studies (including recent studies from our group) show that nocturnal energy expenditure and fat oxidation are independent predictors of longitudinal weight change. It is likely that the RCD+TRF and the standard RCD interventions will have differential effects of nocturnal fuel partitioning which could predict rates of weight regain in the groups.

Polysomnographic (PSG) sleep recording and scoring. During the night spent in the room calorimeter subjects will be fitted with Compumedics Inc Siesta digital sleep recorders. The PSG study will consist of an electrocardiogram (ECG) and electroencephalogram (EEG), electromyogram (EMG), electrooculogram (EOG), and respiratory bands placed over the chest and abdomen. The sleep study will be scored according to revised AASM guidelines. Sleep latencies will be defined as follows: sleep onset latency (SOL), time from lights out to the onset of three continuous epochs of PSG-defined sleep; latency to persistent sleep (LPS), time from lights out to the onset of 10 continuous minutes of PSG-defined sleep; latency to slow wave sleep (SWSL), time from LPS to SWS; and REM sleep latency (REML), time from LPS to REM sleep. Sleep stages (stage 1 sleep, stage 2 sleep, SWS, and REM) will be matched with EE values offset by 2 min to account for the lag-time response of the whole-room calorimeter relative to the timing of the sleep recording.

Behavioral Weight Loss Program (Weeks 1-39).

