Statistical Analysis: Efficacy Testing: Baseline demographic characteristics will be summarized by treatment groups using descriptive statistics. Any imbalance between groups will be examined using two-sample t-tests and Fisher's exact tests as appropriate. The primary analysis will use the ITT principle to test our study hypotheses under practical and realistic conditions when not all participants follow or complete the program. All randomized participants will be analyzed. A linear mixed effect model (LMM) will serve as the primary method to handle missing values. The normality assumptions will be evaluated and transformations used (e.g. square root and log) as appropriate. Change in weight is the primary outcome variable and others will be secondary outcomes. Consequently, no adjustment for multiple outcomes will be applied. P-values <0.05 will be considered significant. No interim analysis is planned. Any imbalance in baseline characteristics between groups that could potentially be a confounding factor for the outcome will be adjusted for in the statistical model (i.e., age, sex, level of PA achieved during intervention). Differences between groups in weight, fat mass, lean mass, MVPA, EI, sleep outcomes, and glucose variability will be compared using a LMM. Specifically, the test of time by group interaction will be used to assess efficacy. Pearson's correlations will be used to assess the relationship between sleep and nocturnal metabolism outcomes and longitudinal weight regain at 6 months. Variability of Major

Outcome Measures: Standard deviation and effect sizes will be determined based on the LMM model estimates to assist with planning the large-scale trial.

G. Summarize Knowledge to be Gained:

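### The planned correlations of nocturnal measures with weight regain have no arm term; if the arms differ on both variables, a pooled correlation is non-zero even with no link within arms

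*Combined protocol and SAP*

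**What the plan says.** All references are to the combined protocol and SAP.

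- **Method.** Section IV.F, Statistical Analysis, says that Pearson "correlations will be used to assess the relationship between sleep and nocturnal metabolism outcomes and longitudinal weight regain at 6 months". Nothing is said about arm, stratification or partial correlation. The covariate rule in the same paragraph concerns baseline imbalance in the statistical model and does not mention the correlations.
- **Threshold.** The same paragraph says "P-values <0.05 will be considered significant".
- **Sample and timing.** Section II, Innovation, gives the sample and the plan as: "subset of subjects (n=5) in each group (RCD and RCD+TRF) following the intervention and correlate these measures with longitudinally determined weight regain at 6 months". Section IV.C, Nocturnal energy metabolism, adds: "We aim to perform approximately n=5 room calorimeter studies per group depending on budget".
- **Feeding at the follow-up chamber stay.** Section IV.C: "Participants in the RCD group will eat all meals within the same 12-hour eating window as was followed at baseline". That schedule puts dinner at T0 + 11.5 h. By contrast, "participants in the TRF group will be asked to eat all food within their chosen 10-hour eating window as follows", with dinner at + 9 h. Participants enter the calorimeter at their habitual bedtime.
- **Expectation.** The rationale in section IV.C calls it likely that the two programmes affect nocturnal fuel partitioning differently, and says this could predict regain by group. Aim 1b asks whether RCD+TRF lowers the risk of regain.

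**The concern.** The rationale for the chamber study is that nocturnal energy expenditure and fat oxidation predict later weight change independently. A correlation that ignores arm cannot show independence from arm. By the protocol's own expectation, arm may be related to the predictor (through the intervention, and through meal timing on the measurement day) and also to the outcome. Two clusters of points, one per arm, displaced on both axes produce a correlation even if the measure says nothing about regain among people in the same arm.

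At stake is interpretation. These results are meant to probe mechanism and help shape a larger trial. A between-arm contrast read as an individual-level predictor could misdirect that planning.

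**Working it through.** **Nothing to reproduce.** The documents give no power, precision or sample-size figure for the correlations.

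**Inputs from the documents.** About 5 per arm, so n=10 if pooled (sections II and IV.C); alpha 0.05 (section IV.F), taken as two-sided because sidedness is not stated; no arm term. At follow-up, dinner relative to T0 is 11.5 − 9 = 2.5 h earlier in RCD+TRF.

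**Assumed inputs.** The arm shifts dx (nocturnal measure) and dy (regain), in within-arm SD units. Data are normal and the within-arm correlation is zero.

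**Step 1: population correlation induced by pooling two equal arms.**

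r = (dx·dy/4) / √[(1 + dx²/4)(1 + dy²/4)]

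With dx = dy = 1: 0.25/1.25 = 0.20. With dx = dy = 2: 1/2 = 0.50. If either shift is zero, the numerator is zero and r = 0.

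**Step 2: critical values**, from |r| = t/√(df + t²).

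- Pooled, n=10, df = 8, t = 2.306: 2.306/√(8 + 5.318) = 0.632.
- Arm-adjusted, n=10, df = 7, t = 2.365: 2.365/√(7 + 5.591) = 0.666.
- Single arm, n=5, df = 3: 0.878.

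**Step 3: chance of p<0.05** (100,000 simulated data sets per row, 5 per arm).

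| dx | dy | Pooled population r | Pooled, p<0.05 | Arm-adjusted, p<0.05 |
|---|---|---|---|---|
| 1 or 2 | 0 | 0 | 4.9% | 4.9–5.0% |
| 0 | 1 | 0 | 5.0% | 5.1% |
| 0.5 | 0.5 | 0.06 | 5.3% | 5.0% |
| 0.8 | 0.8 | 0.14 | 6.6% | 5.0% |
| 1 | 1 | 0.20 | 8.6% | 5.0% |
| 1.5 | 1.5 | 0.36 | 19.0% | 4.9% |
| 2 | 1 | 0.32 | 15.6% | 5.0% |
| 3 | 0.83 | 0.32 | 15.7% | 5.1% |
| 2 | 2 | 0.50 | 37.0% | 5.1% |

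**Step 4: precision.** For an observed r of 0.5 at n=10, Fisher's z gives 0.549 ± 1.96/√7 = 0.549 ± 0.741. Back-transformed, the 95% CI is −0.19 to 0.86.

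**Step 5: a rough scale for dy.** The only weight SDs given are for 12-week loss: 3.7 kg (RCD) and 4.2 kg (assumed for RCD+TRF). Their root mean square is √[(13.69 + 17.64)/2] = 3.96 kg. If regain had that SD (an assumption), 1.5 SD would be 5.9 kg and 2 SD 7.9 kg. For comparison, the assumed mean RCD loss at 12 weeks is 4.1 kg, and the trial's stated detectable difference of 3.5 kg is 3.5/3.96 = 0.88 SD.

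**The case against.** Five points can be made on the other side.

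1. **Pooling is inferred.** A reader might take it that the plan commits to pooling. It does not: section IV.F is silent, and section II counts the subset by group. This stands. But an unqualified Pearson correlation is most naturally pooled, and the by-arm reading leaves n=5, where only |r| above 0.878 reaches p<0.05. Either way the role of arm needs stating.
2. **The feeding schedules alone do no harm.** A reader might infer that different chamber dinners are enough to manufacture a predictor of regain. They are not: with dy = 0 the pooled r is zero and rejection stays near 5%. The documents also report no acute effect, only that differential effects are likely. The 2.5 h gap is relative to T0, which is described differently for the baseline schedule and for RCD+TRF, so the dinner-to-bedtime interval is not fixed at that difference.
3. **The large figures need large shifts.** This stands. On the rough scale above, 19% and 37% require regain differences larger than the whole assumed mean RCD loss. At 0.5 to 0.8 SD the rate is close to nominal. The nocturnal measure has no such scale, however, and a large shift there with a moderate one in regain still gives about 16%.
4. **These rejections are not false positives in the strict sense.** When both variables shift, the pooled correlation really is non-zero. The error lies in reading it as an individual-level link. Part of the stated rationale is itself a between-arm idea, which adjustment removes. That is a reason to show both estimates, not to leave arm out.
5. **The aim is already exploratory**, the chamber stay is optional, and the p<0.05 sentence sits under Efficacy Testing, so applying it to the correlations is an inference. This limits the consequence, but the method is still left open.

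**Conclusion.** The point holds as a minor analysis-choice issue. As written, the correlations cannot distinguish an intervention that moves both variables from a measure that predicts regain within arms, and the protocol anticipates the condition under which that matters. The conclusion rests on the pooled reading and on the arms differing on both variables.

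The size is uncertain because every shift is assumed: negligible at 0.5 SD on both, modest at 1 SD, and substantial only at about 1.5 SD or more on both or with a large shift on one. The documents do not support saying that the artefact will occur, or that 19% to 37% is the expected rate. The effect is confined to the exploratory aim.

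**What to change.** In section IV.F, Statistical Analysis, replace the correlation sentence with text to this effect:

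> The association of each sleep and nocturnal metabolism measure with 6-month weight regain will be estimated adjusting for randomized arm (partial correlation, or regain regressed on the measure plus arm). Any statement that a measure predicts regain will rest on this estimate. The unadjusted correlation will be shown beside it. Both will be given with 95% CIs as hypothesis-generating results, without claims of significance.

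**Cost.** One sentence becomes four, and one degree of freedom is lost. At n=10 the critical |r| rises from 0.632 to 0.666, and the true correlation needed for 80% power rises from about 0.76 to about 0.79. Both analyses are weak at this size, which is why the intervals matter more than the p-values.

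**What it does not solve.** Adjusting for arm removes the between-arm artefact. It does not separate an acute effect of meal timing on the chamber day from a lasting adaptation to the programme; the report should say so.
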